4.13.5 ECG

Standard safety 12-lead ECGs will be performed as shown in the Schedule of Assessments.

The following ECG parameters will be recorded:

- RR-interval (msec).
- QRS-interval (msec)
- PR-interval (msec)
- QT-interval (msec)
- QTc-interval (msec)
- QT-interval corrected using the Fridericia correction formula (QTcF) (msec)
- Heart rate (HR) (beats per minute [bpm])

The ECG will be evaluated by the Investigator as 'Normal', 'Abnormal, NCS' or 'Abnormal, CS'.

All ECG parameters will be listed by participant including changes from baseline.

Baseline is defined in section 4.2.4.

Descriptive statistics for absolute values and changes from baseline will be presented by treatment.

Measurements obtained at Screening and EOS will not be included in the shift tables.

Measurements obtained prior to dosing in each period will be included in the tabulations for the treatment received in that specific treatment period.

The listing of ECG abnormality will be presented separately.

4.13.6 Physical Examination

Physical examinations will include, at a minimum, assessments of the Cardiovascular, Respiratory, Gastrointestinal, Neurological, and Skin systems. Height will also be measured and recorded at Day 1 and weight will be measured and recorded at every visit.

- Investigators should pay special attention to clinical signs related to previous serious illnesses or AEs.
- All physical examinations should include inspection of the injection site.
- Abnormal physical examination findings will be listed.

4.13.7 Other Analysis

4.13.7.1 Columbia-Suicide Severity Rating Scale

The C-SSRS is a suicidal ideation rating scale created by researchers at Columbia University. It rates an individual's degree of suicidal ideation on a scale, ranging from "wish to be dead" to "active suicidal ideation with specific plan and intent."

The scale identifies behaviors that may be indicative of an individual's intent to commit suicide. The C-SSRS is used extensively across primary care, clinical practice, surveillance, research, and institutional settings and is part of a national and international public health initiative involving the assessment of suicidal ideation and behavior. The C-SSRS requires no mental health training to administer it. The C SSRS will be administered by qualified, trained raters.

The Baseline version will be administered at Screening and at subsequent visits the “C-SSRS Since Last Visit” version will be administered.

C-SSRS and Domain wise scores will be summarized by treatment arm and visit. C-SSRS will be listed by participant.

4.13.7.2 Exploratory Analyses

The descriptive statistics of participant’s alcohol consumption measured by TLFB will be present for each arm and study days. Each of the drinks will be multiplied by 14g to achieve the alcohol amount. [3]. Change of baseline from both day -1 and screening visit will be presented for each arm. The mean difference and its 95% CI will be presented for the change from baseline of alcohol consumption for each assessment day. Similar analysis will also be performed for total alcohol consumed from baseline.

For PEth descriptive statistics will be present for assessment days. The mean difference and its 95% CI will be presented for the change from baseline of PEth levels for each assessment day.

By participant listings will be present for the exploratory analyses for SP.

4.13.8 Daylight Saving Time (DST):

Not applicable.

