^a At the time of discontinuation for the study, an early termination (ET) visit should be conducted, if possible.

- ^b Participants with significant symptoms at the Day 168 EIA will be followed for an additional 4 weeks at the discretion of the Investigator.
- ^c Visits without a specified window are to be conducted relative to the associated scheduled visit. For example, Day 28 will always be the day prior to the Day 29 visit, regardless of where Day 29 falls within the \pm 2-day visit window.
- ^d Screening tests positive for cannabis are not exclusionary.
- ^e To include hematology (CBC with differential and RBC indices), clinical chemistry, coagulation panel, urinalysis, viral serology, HbA_{1c}, and FSH (as indicated). See [Section 10.2](#) for a complete list of parameters.
- ^f Baseline genetic testing for *ALDH2* mutations. Participation is optional; participants who do not wish to undergo genotyping may still participate in the study.
- ^g The Baseline version will be administered at Screening and at subsequent visits the “C-SSRS Since Last Visit” version will be administered. Participants who exhibit signs of Suicidal Ideation or Behavior (SIB) should undergo a risk assessment. All factors contributing to SIB should be evaluated and consideration should be given to discontinuation of study intervention.
- ^h TLFB will be completed for the 2-week period that precedes each study visit, including Screening.
- ⁱ Pregnancy testing required only in female participants. If a urine pregnancy test is positive, confirm with serum pregnancy test. Local laboratory may be used. Female participants must have a negative pregnancy test prior to overnight admission.
- ^j Testing to be performed at the site upon admission. Participants with a positive SARS-CoV-2 test will not be admitted to clinic and will not receive study intervention or undergo EIA. Other assessments not requiring clinic admission (i.e., safety assessments) will be performed. Testing will be performed per site standard processes.
- ^k Study participants are to refrain from drinking alcohol and using cannabis for 24 hours prior to each EIA. Participants with a positive urine-drug or breath-alcohol test will not be admitted to clinic and will not undergo EIA. Participants with a positive urine drug test on Day –1 will be excluded from the study.
- ^l Participants must be fasting for at least 3 hours prior to admission to the clinic.

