- ^m Participants may be discharged from clinic following collection of the 24-hour postdose PK sample. Participants will return to clinic for collection of PK samples at 72 hours postdose on Days 4 and 32.
- ⁿ EIA will be conducted on the first day of the visit once all other assessments for that day have been completed. A total of 10 EIAs will be conducted. The timing of assessments and ethanol administration are detailed in [Table 3](#).
- ^o On dosing days, ECGs will be conducted approximately 30 minutes predose and 15-to-30 minutes postdose. If multiple assessments are due, the order of assessment should be ECG, vitals, PK, and then other assessments; with PK sample collection occurring at the nominal time. At Screening and EOS, one ECG will be performed. Screening ECGs may be repeated one time for determination of eligibility.
- ^p Blood pressure, if out of range at Screening, may be repeated one time for determination of eligibility.
- ^q Blood pressure and pulse rate to be recorded 15 (\pm 5) minutes postdose.
- ^r Height will be measured and recorded at Screening. Weight will be measured and recorded at every visit.
- ^s Sample to be collected prior to ethanol administration.
- ^t Hematology to include complete blood count with differential and RBC indices. See [Section 10.2](#) for a complete list of parameters.
- ^u See [Section 10.2](#) for a complete list of parameters.
- ^v Blood samples for complement testing to be collected predose and 2, 8, and 24 hours postdose on Day 1 and Day 57.
- ^w Blood sample for ADA testing to be drawn at same time as predose PK sample on Day 1.
- ^x Plasma samples for PK analysis to be collected predose and at 1, 2, 4, 6, 8, 24, and 72 hours postdose (exception: no 72-hour PK sample is required at Day 57). A single sample will be collected on Day 168. If multiple assessments are due, the order of testing should be ECG, vitals, PK, and then other assessments, with the PK sampling performed preferably at the nominal time point. A \pm 15-minute window will be allowed for collections at 1, 2, 4, 6, and 8 hours postdose. A \pm 30-minute window will be allowed for collection at 24 hours postdose. A \pm 60-minute window will be allowed for collection at 72 hours postdose.
- ^y Participants to record any symptoms associated with use of alcohol outside of in-clinic EIAs. Diary to be issued at time of discharge from clinic and collected and reviewed upon return to clinic.

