8.1.1. Alcohol Consumption via Timeline Follow Back

Participants will complete the TLFB at screening and throughout the study period to capture any change in drinking behavior. At every visit, the TLFB will be used to assess each participant's alcohol consumption for the 2-week period that precedes the study visit.

The TLFB was developed as a procedure to aid recall of past drinking ([Sobell & Sobell, 1992](#)). Currently, self-reports are the only viable method for retrospectively measuring drinking with any precision. Alternative methods exist, but they are either impractical (e.g., continuous direct observation), fraught with problems (e.g., alcohol sweat patches), or they only measure very recent drinking (e.g., blood alcohol tests). TLFB stands as the most exhaustively evaluated method that can be used to retrospectively assess drinking behavior over time.

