9.4.4. Exploratory Endpoint(s)

The exploratory endpoint of change in drinking amounts will be assessed using the TLFB and by analysis of blood levels of phosphatidylethanol.

Average daily drinking amounts over each 2-week period after the start of dosing will be compared to the amount during the 2-week period before first dose. Change in drinking amounts for each postdose period will be evaluated in connection with changes in EIA-induced peak symptoms and plasma acetaldehyde levels during the preceding EIA.

Other exploratory analyses will be conducted as deemed appropriate and will be detailed in the SAP.

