4.2.4 Baseline

Baseline is defined as the last non-missing measurement prior to the date and time of the dose of study intervention.

For the exploratory analysis using TLFB, baseline is the mean alcohol level as measured on Day -1.

No imputation will be done for missing baseline value for derivation of change from baseline or summary tables and shift tables.

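### SAP 4.13.7.2 does not keep ethanol served in the EIAs out of the TLFB amounts, so change from baseline at Days 14 to 84 may be inflated

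*SAP*

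**What the plan says.** **What the TLFB covers.** The Schedule of Activities (Protocol 1.3) states: "TLFB will be completed for the 2-week period that precedes each study visit, including Screening". Protocol 8.1.1 likewise has it assess alcohol "consumption for the 2-week period that precedes the study visit". Neither place limits it to drinking away from the clinic. The symptom diary, by contrast, is limited in that way: "Participants to record any symptoms associated with use of alcohol outside of in-clinic EIAs".

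**When ethanol is served.** "A total of 10 EIAs will be conducted". On timing, the footnote for dosing and end-of-study visits reads "EIA will be conducted on the first day of the visit once all other assessments for that day have been completed", and the footnote for the other visits is similar. So a visit's TLFB comes before that visit's own EIA. Protocol 8.6.1 caps the EIA ethanol at 56 g for men and 48 g for women, taken in four aliquots.

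**How the TLFB is analysed.** SAP 4.2.4: "For the exploratory analysis using TLFB, baseline is the mean alcohol level as measured on Day -1". SAP 4.13.7.2: "Each of the drinks will be multiplied by 14g to achieve the alcohol amount". That section reports change from Day -1 and from screening for each arm, a mean difference with 95% CI at each assessment day, and a similar analysis of total alcohol. Protocol 9.4.4 defines the comparison differently: average daily drinking in each two-week period after dosing starts "will be compared to the amount during the 2-week period before first dose". Protocol 4.1 has the questionnaire completed every two weeks, although visits after Week 12 are four weeks apart.

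**The concern.** The endpoint exists to show whether participants choose to drink differently (Protocol 8.1). EIA ethanol is set by the protocol and says nothing about that choice. EIAs are about 14 days apart up to Day 84 and 28 days apart afterwards, while the look-back stays at 14 days. Clinic ethanol can therefore enter the early windows but not the baseline or the late ones. A term that switches on and off with the visit schedule does not cancel in a per-arm change from baseline.

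Two features add to this. Protocol 9.4.4 relates each period's change in drinking to symptoms and acetaldehyde at the preceding EIA. If alcohol was stopped early in a symptomatic participant, the next window holds less clinic ethanol, which could create a mechanical association. And with 4 placebo participants, one person's 56 g in or out of a window moves the arm mean by 56/4 = 14 g.

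**Working it through.** **1. Reproduce the number of EIAs.** Days -1, 14, 28, 42, 56, 70, 84, 112, 140 and 168 make 10, matching the stated total. Days 112 and 140 are inferred from Weeks 16 and 20 (16 × 7 and 20 × 7), because the schedule table is broken in the text.

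**2. Place each EIA against the look-backs.** SAP 4.2.2 has no Day 0. Take the window as the 14 days ending the day before the visit.

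| TLFB visit | Window (days) | EIA inside |
|---|---|---|
| -1 (baseline) | ends before Day -1 | none |
| 14 | -1 to 13 | Day -1 |
| 28 | 14 to 27 | Day 14 |
| 42 | 28 to 41 | Day 28 |
| 56 | 42 to 55 | Day 42 |
| 70 | 56 to 69 | Day 56 |
| 84 | 70 to 83 | Day 70 |
| 112 | 98 to 111 | none |
| 140 | 126 to 139 | none |
| 168 | 154 to 167 | none |

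The screening window also holds none. Every included EIA lies on the first day of its window.

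**3. Gross size if clinic drinks are reported.** 4 drinks × 14 g = 56 g; 56/14 days = 4.0 g/day. A woman reporting 4 drinks is also booked 56 g, although at most 48 g was served (8 g too many). Relative to two-week intake at the eligibility limits (Protocol 5.1):
- Men, 5 to 20 drinks/week: 4/10 = 40% down to 4/40 = 10%.
- Women, 5 to 14 drinks/week: 4/10 = 40% down to 4/28 = 14%. On the 48 g served, 48/140 = 34% down to 48/392 = 12%.
- Step from Day 84 to Day 112 in a man with constant drinking: 4/14 = 29% down to 4/44 = 9% of the Day 84 amount.

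**4. Visit shifts.** The EIA stays inside only if the gap between visits is 14 days or less. With ±2 days at both visits and every shift equally likely (an assumption), that is 15 of 25 combinations, or 60%. With ±3 days at both it is 28 of 49, or 57%. For the 28-day gaps the shortest possible gap is 28 - 6 = 22 days with ±3 at both ends, or 28 - 3 - 7 = 18 with ±7 at one end. An EIA therefore never enters those windows.

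**5. Usual drinking displaced by clinic stays.** Assume usual intake of r drinks/week, evenly spread and not made up later, with d clinic days in the window. Net excess = 56 - 14 × (r/7) × d = 56 - 2rd grams.
- Day 28, 56 and 84 windows (d = 1): +46 g at r = 5, +36 g at r = 10, +16 g at r = 20.
- Day 14, 42 and 70 windows, which include the stays around dosing (d = 2 to 3): +36 to +26 g at r = 5, +16 to -4 g at r = 10, -24 to -64 g at r = 20.

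**6. The protocol's baseline.** Read by calendar, the two weeks before first dose are Days -14 to -1, which include the Day -1 EIA. The SAP's Day -1 look-back does not. The two documents therefore disagree on whether the baseline contains an EIA.

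**The case against.** The strongest reply is that the effect is conditional. No text says that participants report clinic drinks in the TLFB. The instrument is meant to capture drinking behaviour, and training material outside these documents may already exclude them. That stands: the documents leave the matter open, and the size in step 3 is what follows if the drinks are reported.

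Placement is also fragile. A gap of 15 days moves the EIA out, and so does a window that ends on the visit day itself. Displacement can cancel or reverse the excess in the Day 14, 42 and 70 windows. These points stand as well. They make the error irregular rather than absent: under the even-drinking assumption, the Day 28, 56 and 84 windows keep a positive net excess over the whole eligible range.

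Both arms follow the same EIA schedule, so a DCR-AUD minus placebo difference is largely unaffected. The exception is where EIAs are stopped early (Protocol 8.6.1.3) or withheld (Protocol 7.3.4) more often in one arm. The SAP does not say whether its mean difference is within or between arms.

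A reader might infer that the plan would produce a false late fall in drinking that imitates a delayed drug effect. The documents do not support that. The SAP baseline and the Day 112, 140 and 168 windows are all free of EIA ethanol, so constant drinking gives zero change there. The late drop appears only when Day 112 is set against Day 84, a contrast that the SAP does not plan. The delay discussed in Protocol 4.2 concerns acetaldehyde and symptoms, not drinking.

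**Conclusion.** The gap is real but small. Taken literally, the plan lets study-served ethanol into the TLFB amounts at Days 14 to 84 and not at baseline or after Day 84. The per-arm change from baseline can then show a false early rise or hide a real early fall, followed by a step down after Day 84.

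The gross maximum is 56 g per window (4 g/day). After displacement, the Day 28, 56 and 84 windows keep +46 g at 5 drinks/week and +16 g at 20 drinks/week. In the Day 14, 42 and 70 windows the net effect can take either sign. These figures rest on clinic drinks being reported, nominal visit days, a window ending the day before the visit, and evenly spread usual drinking. The endpoint is exploratory and descriptive in 16 participants, so this is a desirable clarification and not a threat to the trial's main conclusions.

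**What to change.** In SAP 4.13.7.2, compute average daily TLFB drinking over non-clinic days only. Drop EIA and confinement dates from both the drinks and the day count. Apply the same rule to total alcohol consumed, expressed per 14 days so that windows with fewer usable days remain comparable.

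Do not subtract nominal grams served. If clinic drinks were never reported, subtraction would create a false fall, and neither document shows that grams actually consumed are recorded.

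Define each 14-day window by start and end dates. Reconcile the Day -1 baseline in SAP 4.2.4 with the period before first dose in Protocol 9.4.4, and both with the two-weekly completion in Protocol 4.1. State whether the mean difference is within or between arms.

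The cost is a few sentences, recorded through the modification form that SAP Section 1 provides, plus a date filter. Windows at Days 14 to 84 shrink from 14 days to about 11 to 13. The rule needs TLFB entries by day, which the documents do not confirm. If only two-week totals were kept, the report should state whether clinic drinks were included.

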5.3. Lifestyle Considerations

Alcohol, Tobacco, and Cannabis

1. Study participants are to refrain from drinking alcohol for 24 hours prior to each EIA and must have a negative breath-alcohol test on the day of the study visit.
2. Study participants will be advised to avoid consuming more than 4 drinks during any drinking session outside of in-clinic EIAs.
3. Study participants will be instructed to stop drinking at the onset of any ethanol reaction symptoms during outside drinking sessions.
4. Tobacco/nicotine use is not restricted.
5. Study participants are to refrain from using cannabis for 24 hours prior to each EIA and must have a negative urine-drug test on the day of the study visit.

Activity

1. Study participants should abstain from strenuous exercise for 24 hours before each blood collection for clinical laboratory tests. Participants may participate in light recreational activities (e.g., walking at a pace < 3 miles per hour, shopping, watering plants) in that 24-hour time period.

Meals and Dietary Restrictions

1. For each EIA study visit, participants will be required to fast for at least 3 hours and then will be fed a standardized meal in the clinic prior to administration of ETOH for the EIA.

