8.1. Efficacy Assessments

This is a Phase 1 study with the primary objective of evaluating safety. Pharmacokinetic and PD assessments are detailed in [Section 8.5](#) and [Section 8.6](#), respectively.

As the study participants are HV not diagnosed with AUD, no true assessment of efficacy can be made. However, study participants may be inclined to change their alcohol intake should they experience physiologic symptoms associated with increased acetaldehyde while drinking. As such, 2 assessments of alcohol intake, TLFB and PEth, will be considered in exploratory analyses.

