4.20 Determination of Sample Size

No formal sample size estimations were performed. The sample size of 16 participants (12 active and 4 placebo) was considered sufficient to provide an initial assessment of the safety profile of DCR-AUD in HVs, and adequate for the purpose of describing PK/PD data in HVs.

The sample size is based on clinical rather than statistical considerations.

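### SAP 4.13.7.2 plans 95% CIs for change in drinking and PEth without naming a DCR-AUD versus placebo contrast, so a change common to both arms could be misread as a drug effect

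*SAP*

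**What the plan says.** The exploratory objective is to explore change in alcohol consumption after treatment with DCR-AUD. Protocol 8.1 gives the rationale: "study participants may be inclined to change their alcohol intake should they experience physiologic symptoms associated with increased acetaldehyde while drinking". The two measures are TLFB drinking and PEth.

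SAP 4.13.7.2 handles TLFB in two steps. First: "Change of baseline from both day -1 and screening visit will be presented for each arm". Then: "The mean difference and its 95% CI will be presented for the change from baseline of alcohol consumption for each assessment day". A similar analysis is planned for total alcohol consumed.

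For PEth it says: "For PEth descriptive statistics will be present for assessment days". It continues: "The mean difference and its 95% CI will be presented for the change from baseline of PEth levels for each assessment day". Treatment arm is not mentioned.

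Protocol 9.4.4 describes a comparison over time: average daily drinking in each two-week period after dosing starts "will be compared to the amount during the 2-week period before first dose". Protocol 9.1 plans no inferential tests. On size, SAP 4.20 says: "The sample size of 16 participants (12 active and 4 placebo) was considered sufficient".

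**The concern.** These are the only intervals planned for drinking, and the text does not say what they estimate. If they are within-arm or pooled, zero means that drinking did not change during the study. The question of interest is whether DCR-AUD changed it, and only the placebo arm can separate the two.

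Several features of the study act on both arms:

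- Protocol 5.3: "Study participants will be advised to avoid consuming more than 4 drinks during any drinking session outside of in-clinic EIAs". Inclusion criterion 4 allows up to 8 drinks in a day at entry, so the advice could lower intake whatever the treatment.
- Overnight clinic stays fall inside some of the two-week TLFB look-back windows.
- Each EIA gives up to 56 g of ethanol to men and 48 g to women. Protocol 8.1.2 says that PEth can be detected for up to a month after a single intake. PEth samples are drawn before the EIA ethanol of the same visit, so a sample taken before the first EIA carries no study ethanol, while later samples may. This pushes PEth up in both arms.

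The net shared change could be a fall or a rise. An active-arm interval that excludes zero could be taken as a first sign that the drug alters drinking. The 3:1 allocation adds to the risk: the same change is far more likely to exclude zero in 12 people than in 4, and the pair of intervals could then look like a drug response with a quiet placebo arm.

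**Working it through.** **Inputs.** 12 active and 4 placebo (SAP 4.20); 16 × 3/4 = 12 and 16 × 1/4 = 4 agree with 3:1. Interval level 95% (SAP 4.13.7.2). The plan gives no precision or power figure to reproduce. It gives no SD for change in TLFB or PEth, so results are in units of that SD. Assumed: normal changes, equal SD in both arms, no dropout.

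**Which contrast the text supports.** Three points favour within-arm for TLFB: the preceding sentence is by arm; Protocol 9.4.4 compares with the participants' own pre-dose period; and where the SAP wants a treatment comparison (the biomarker ANOVA in 4.12.5) it names DCR-AUD and placebo. One point leaves the other reading open: a mean difference for change from baseline is also ordinary wording for a between-arm difference.

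**Half-widths (SD units).**

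- Within arm, t(0.975, n−1)/√n. Active: 2.201/√12 = 0.64. Placebo: 3.182/√4 = 1.59. Ratio 2.5.
- Pooled over 16: 2.131/√16 = 0.53.
- Between arms, t(0.975, 14) × √(1/12 + 1/4) = 2.145 × 0.577 = 1.24.

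With equal observed SDs, the same observed mean change anywhere between 0.64 and 1.59 SD excludes zero in the active arm and not in placebo.

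**Chance that the interval excludes zero with no drug effect.** For a true change of d SD shared by both arms, this is the two-sided tail of a noncentral t with n−1 degrees of freedom and noncentrality d√n. The active-only column is P(active) × (1 − P(placebo)). At 0.5 SD, 0.3528 × (1 − 0.1113) = 0.314.

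| Shared change | Active, n=12 | Placebo, n=4 | Active only | Pooled, n=16 | Between arms |
|---|---|---|---|---|---|
| 0.25 SD | 12% | 7% | 11.6% | 16% | 5% |
| 0.5 SD | 35% | 11% | 31.4% | 46% | 5% |
| 0.75 SD | 66% | 19% | 53.5% | 80% | 5% |
| 1.0 SD | 88% | 29% | 62.8% | 96% | 5% |

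A shared change cancels from the between-arm difference, which is why the last column is constant. A simulation of 200,000 trials gave 5.0% at shared falls of 0, 0.5, 1.0 and 1.5 SD.

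Beyond 1.0 SD the active-only pattern becomes rarer, at 47% for 1.5 SD and 24% for 2.0 SD, because placebo then excludes zero as well.

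**What the between-arm interval can detect.** For true differences of 0.5, 1.0, 1.5 and 2.0 SD it excludes zero about 13%, 36%, 68% and 90% of the time.

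**The case against.** The best defence is that *mean difference* may already mean DCR-AUD minus placebo. Change for each arm has just been presented, so a further mean difference could be the between-arm step. If so, the false-signal argument falls away. This stands in part: the SAP does not expressly define a within-arm interval, and the defect is an unspecified contrast. It does not settle the matter, because an analyst following the text could produce any of three intervals, and Protocol 9.4.4 points to the within-arm one.

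A reader might also infer four stronger claims that the documents do not support:

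- *That a shared fall would show as an effect in the active arm and none in placebo.* It could. The pattern occurs in about 63% of trials at a 1.0 SD change and less often at the other sizes computed. At 0.5 SD the likeliest result is that neither interval excludes zero, at 58%.
- *That drinking must fall in both arms by design.* Adherence to the advice is unknown, and the documents do not say whether TLFB counts EIA ethanol; counting it could offset a fall or turn it into a rise. At nominal days the Week 16, 20 and 24 look-backs contain no clinic stay.
- *That PEth is pooled.* The text is silent on arm. Pooling is possible but not stated.
- *That an interval is planned from the screening baseline.* SAP 4.2.4 sets Day -1 as the TLFB baseline, and screening appears only in the by-arm summary sentence.

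Finally, the endpoints are exploratory, Protocol 8.1 disclaims any true assessment of efficacy, and TLFB placebo summaries will sit beside the active ones. That limits the harm. It does not remove the need to say what a planned 95% CI estimates.

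**Conclusion.** The point holds as an unspecified contrast with a misleading default. No DCR-AUD versus placebo comparison is named for TLFB or PEth. The natural TLFB reading is within-arm, and the PEth text permits pooling. Either leaves the placebo control out of the interval while shared study procedures can move the outcome up or down.

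Under a shared change of 0.25 to 0.75 SD and no drug effect, the active-arm interval excludes zero in 12% to 66% of trials, against 5% for a between-arm interval. These figures rest on normal changes, equal SDs and no dropout. The size of any shared change is assumed, because the documents give neither it nor the SD. The concern does not touch the primary safety objective.

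**What to change.** In SAP 4.13.7.2, replace the two interval sentences with one rule covering TLFB drinking, total alcohol consumed and PEth: for each assessment day, present DCR-AUD minus placebo in mean change from baseline, with its 95% CI. The baseline is Day -1 for TLFB and the general pre-dose rule for PEth, both as in SAP 4.2.4. State that PEth is summarised by arm. Keep within-arm changes, and change from screening, as descriptive by-arm summaries.

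Baseline adjustment is optional. It would require SAP 4.16, which now marks covariate adjustment as not applicable, to be updated. The 1.24 SD half-width above is for the unadjusted difference.

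The cost is SAP wording and one contrast per table, with no new data. Because the SAP is already final, the change belongs in a new version or in the modification form named in SAP section 1. The drawback is low precision: with 12 versus 4 the interval is about twice as wide as the active-arm one (1.24/0.64 = 1.9) and will often be inconclusive. That width is what this design can say about a drug effect on drinking.
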